5.6 APPROPRIATENESS OF MEASUREMENTS

The scheduled measurements will allow monitoring of changes in vital signs, standard laboratory values, and ECG variables that might occur as a result of administration of trial medication. The safety assessments are standard, are accepted for evaluation of safety and tolerability of an intravenously administered drug, and are widely used in clinical trials. The pharmacokinetic parameters and measurements outlined in [Section 5.3](#) are generally used assessments of drug exposure. The biomarkers and pharmacogenomic parameters are outlined in [Section 5.4](#) are of exploratory nature only.

Information about race should be obtained from all study participants as allowed by local regulations. This is because the prevalence and characteristics of psoriasis may differ between patients of different racial origin. It will thus be worthwhile to assess if patients of different race will respond differently to the study treatment.

6. INVESTIGATIONAL PLAN

6.1 VISIT SCHEDULE

All patients are to adhere to the visit schedule specified in the [Flow Chart](#). Each visit date (with its window) is to be counted from Day 1 (V2).

All deviations from the planned visit schedule are to be documented. If any visit has to be rescheduled, subsequent visits should follow the original visit date schedule. Additional visits for the purpose of retesting of laboratory parameters or AE monitoring may be included as deemed necessary by the investigator.

For detailed description of the trial procedures, please refer to the Flow Chart.

Details relating to study drug administration are provided in [Section 4.1.4](#).

6.2 DETAILS OF TRIAL PROCEDURES AT SELECTED VISITS

Study procedures to be performed at each visit are listed in the Flow Chart and respective sections of this protocol. Refer to [Section 5](#) for explanations of the specified assessments and procedural details.

Based on the investigator's clinical judgment, patients may be hospitalized prior to, during or following first study drug administration. If so, patients will perform the needed visits as inpatients. Subsequent visits will be conducted in accordance with the protocol and the investigator's judgment (For details, see Flow Chart and [Section 3.1](#)).

The patients' questionnaires (PSS, [REDACTED] pain VAS, FACIT-Fatigue, [REDACTED] are to be completed by the patient on his/her own in a pre-specified order in a quiet area/room before any other visit assessments or treatments, and, if possible, before any interaction with the investigator or other members of the study team, and, without any help from or interpretation by other people. If the patient is too sick to complete the questionnaires him/herself but is able to reply verbally, a member of the study team should read the instructions, questions, and response options aloud to the patient and collect the patient's verbal response in as neutral and unbiased a manner as possible. If this is not possible either, the questionnaires are not to be completed. The mode of administration should be documented in the electronic Case Report Form (eCRF).

At each applicable visit (see Flow Chart), the order of completion for PROs is recommended to be as follows:

- PSS
- [REDACTED]
- pain VAS

Separate from the PROs above, the evaluation of efficacy assessments (GPPGA, GPPASI, [REDACTED] for a patient are to be conducted by the same physician throughout the study.

6.2.1 Screening period

Screening (Visit 1):

After patients have been informed about the trial, written informed consent in accordance with GCP and the local legislation must be obtained prior to performing any study related procedures.

Once consent is obtained, the patient is considered to have started the screening process, and is assigned a unique patient number by the IRT system. The patient is to be recorded on the enrolment log and be registered in the IRT system as a screened patient. Study requirements, including the procedure for the follow-up of prematurely withdrawn patients, must be fully explained to the patient and written informed consent obtained prior to initiating any study-related evaluation. The importance of staying in the study until completion of all requirements is to be emphasized. No study procedures are to be done unless the patient has provided consent to take part in the study.

Demographics:

Informed consent date, gender, ethnicity and race (if allowed by local law) will be collected and reported in the eCRF.

Baseline Conditions:

Chronic diseases, current observable conditions, any new clinically relevant findings discovered from the physical examination, ECG, safety labs, and any condition requiring therapy (excluding GPP) will be reported on the Baseline Condition eCRF page.

Infection screening:

Infection testing will include tuberculosis, hepatitis B, hepatitis C, and HIV assessments (see [Table 5.2.3.1](#)). Please also refer to applicable exclusion criteria in [Section 3.3.3](#) for details regarding handling of infection test results for patients screened while having a flare (inclusion 1b and 1c).

Medical History:

Information on clinically significant previous and concomitant illnesses, other than GPP, or any clinically significant signs or symptoms that are present before informed consent, or pre-existing conditions identified through findings from assessments and examinations done during the screening visits will be recorded as medical and surgical history at screening. Regarding the GPP, a detailed history of the disease including evidence of systemic symptoms during a GPP flare in the past (i.e. fever, asthenia, myalgia, elevated C-reactive protein, leukocytosis with peripheral blood neutrophilia) and information of histopathological confirmation of diagnosis will be collected and reported in the eCRF. Also, previous and concomitant treatment for GPP will be recorded.

Mutation status:

Information on the presence or absence of IL36RN mutation (if available) will be collected in patient's historical data and reported in the eCRF.

Review of inclusion/exclusion criteria:

Selection criteria will be reviewed carefully.

IRT:

All patients who are screened must be registered with IRT.

Re-screening:

If a patient results in a screen failure (i.e. does not meet the eligibility criteria, or does not flare within the 6 month screening period) the patient must be registered as a screen failure in IRT system. However, re-screening of a previously screen failed patient will be permitted once. Upon re-screening, the patient will be assigned a new patient number. Details of IRT procedures can be found in the IRT manual located in the Investigator Site File (ISF).

For the comprehensive list of the trial procedures required at the Screening Visit (Visit 1) please refer to the [Flow Chart](#).

6.2.2 Randomization Visit and Treatments

Patients will be randomized to receive a single dose of 900 mg BI 655130 or placebo (2:1) at Visit 2.

Please refer to [Section 3.3.4](#) for details regarding criteria for initiation of treatment with BI 655130.

In cases where Visit 1 and Visit 2 are greater than 6 weeks apart, it is recommended that patient is asked to re-confirm (verbally) his/her consent to participate in the trial and this verbal re-consent must be documented. The first study drug administration is at Visit 2 (Day 1).

For information pertaining to PK, ADA/Nab, and biomarkers, see [Sections 5.3](#) and [5.4](#).

For information pertaining to laboratory tests, ECG, vital signs, local tolerability, and physical examination, see [Sections 5.2.1](#) to [5.2.5](#).

Fasting is not required for blood sampling. Pharmacogenomic genotyping for targeted GPP-causing mutations (IL36RN, CARD14, AP1S3) are to be performed for all patients (see [Section 7.3.7.2](#)). DNA banking is optional and is only to be done for patients who have provided informed consent for this specific procedure.

Skin lesion photographs will be taken at all visits on site and are to be taken prior to any skin biopsies or study drug administration.

Skin biopsies (if applicable) and venipuncture (i.e. safety laboratories, PK, ADA/Nab, biomarkers) should be the last procedures done prior to study drug administration.

Study drug allocation via the IRT system and administration of study drug should be the last activity at Visit 2 with the exception of local tolerability and post dose vital signs assessments.

For women of child-bearing potential, pregnancy testing will be done as specified in the [Flow Chart](#).

6.2.2.1 Clinical monitoring after study drug administration

During i.v. drug administration, vital signs will be assessed pre-dose, at approximately 5 minutes after the end of infusion, and 120 minutes after the end of infusion. Patients should be closely monitored for signs and symptoms of hypersensitivity reactions for approximately 2 hours after doses are administered. Hypersensitivity reactions should be treated according to medical standards.

6.2.2.2 Unscheduled visits

During the treatment period patients may be seen at an unscheduled visit if they experience worsening of the disease, recurrence of GPP flare, or have AEs that in the opinion of the investigator need intervention (e.g. escape or rescue treatment) or repeated laboratory testing.

The unscheduled visit may include additional collection of blood samples for safety reasons. The unscheduled visit may also include additional assessments deemed necessary by the investigator such as laboratory samples, ECGs, or other procedures that were missed at a previous visit. All unscheduled visits (including the reason for the visit) should be described and documented in the medical/source record, and in the eCRF.

6.2.3 Follow up period and trial completion

After receiving the single dose at Visit 2, patients will be followed for 12 -28 weeks depending on treatment response. Refer to [Section 3.1](#) for details.

For all randomized patients termination of trial medication and trial completion must be recorded on the corresponding eCRF.

For the comprehensive list of the trial procedures required during the follow-up period, please refer to [Flow Chart](#).

Trial Completion:

Trial completion is defined as a patient having reached the EoS visit within the specified window per protocol.

Treatment Completion:

Treatment completion is defined as a patient receiving the whole amount of prepared dose on D1.

Early Treatment Discontinuation:

In case the infusion of study drug is permanently discontinued before the whole amount of prepared solution has been administered to the patient, every effort should be made to keep the patient in the trial and complete all of the remaining study visits. If this is not possible, assessments of the primary and key secondary endpoints at V9 (Wk1), V12 (Wk4) and EoS Visit (V14 or V15 or V16 as applicable) should be completed or at a minimum an early EoS visit. Please refer to the Flow Chart.

Early Trial Discontinuation:

A patient not having reached the EoS visit within the specified window per protocol (e.g. due to withdrawal of consent, lost to follow-up, death etc.).

An open-label extension trial is planned, see [Section 3.1](#) for details.

7. STATISTICAL METHODS AND DETERMINATION OF SAMPLE SIZE

7.1 STATISTICAL DESIGN – MODEL

This trial is designed as a randomized, parallel-group, double-blind, and placebo-controlled trial with one active dose of BI 655130 in patients with GPP presenting with an acute flare of moderate to severe intensity.

The primary objective of this trial is to evaluate the efficacy, safety and tolerability of a single i.v. dose of BI 655130 in comparison to placebo at Day 1. The primary analysis, on each of the binary, primary endpoint, achievement of a GPPGA pustulation subscore of 0 at Week 1, and key secondary endpoint, achievement of a GPPGA of (0, 1) at Week 1, where any use of escape medication prior to observing the endpoint is considered to be a non-response, will compare the proportion of patients who achieve a response on BI 655130 to Placebo. Given the small sample size proposed to be used in this trial, an exact statistical test, the Suissa-Shuster Z-pooled test, will be used to perform the primary analysis. Confirmation of efficacy is then given if the proportion of patients achieving a response on the primary endpoint is statistically significantly higher for BI 655130 than for placebo. Formal statistical hypothesis testing will be performed at an overall 1-sided alpha level of 0.025.

Stratification of randomization will be performed in this trial for Japan versus non-Japan. This stratification is implemented for operational purposes only and is not intended to be used as an adjustment factor in the primary analyses of efficacy (see [Section 7.6](#)).

7.2 NULL AND ALTERNATIVE HYPOTHESES

The null and alternative hypotheses are described below. Statistical testing will be performed based on one-sided hypotheses and p-values.

Test of the Primary Endpoint

The null hypothesis for the primary endpoint, the proportion of patients achieving a GPPGA pustulation subscore of 0, at Week 1 is

H_{01} : Effect of BI 655130 on the proportion of patients achieving a GPPGA pustulation subscore of 0 at Week 1 (where any prior use of escape medication will be considered to represent a non-response) \leq Placebo;

versus the alternative hypothesis

H_{02} : Effect of BI 655130 on the proportion of patients achieving a GPPGA pustulation subscore of 0 at Week 1 (where any prior use of escape medication will be considered to represent a non-response) $>$ Placebo.

Only if the null hypothesis, H_{01} of the primary endpoint is rejected, will the efficacy of BI 655130 in the treatment of acute GPP flares be confirmed.

Test of the Key Secondary Endpoint

Further hypothesis will be tested on the key secondary endpoint in a hierarchical manner if the null hypothesis of the primary endpoint H_{01} has been previously rejected.

The null hypothesis for the key secondary endpoint, the proportion of patients achieving a GPPGA score of (0, 1), at Week 1 is

H_{11} : Effect of BI 655130 on the proportion of patients achieving a GPPGA of 0 or 1 at Week 1 (where any prior use of escape medication will be considered to represent a non-response) \leq Placebo;

versus the alternative hypothesis

H_{12} : Effect of BI 655130 on the proportion of patients achieving a GPPGA of 0 or 1 at Week 1 (where any prior use of escape medication will be considered to represent a non-response) $>$ Placebo.

No adjustment of the 1-sided alpha-level of 0.025 is necessary.

Test of the Secondary Endpoints

Further hypotheses will be tested on the following secondary endpoints in a hierarchical manner if both null hypotheses of the primary endpoint and key secondary endpoint, H_{01} and H_{11} , have been previously rejected. Note that the study is not further powered for the performance of these additional statistical comparisons.

The null hypothesis for the secondary endpoint, the proportion of patients achieving a GPPASI 75 at Week 4 is

H_{21} : Effect of BI 655130 on the proportion of patients achieving a GPPASI 75 at Week 4 (where any prior use of escape medication/OL BI 655130 at D8/rescue medication with BI 655130 will be considered to represent a non-response) \leq Placebo;

versus the alternative hypothesis

H_{22} : Effect of BI 655130 on the proportion of patients achieving a GPPASI 75 at Week 4 (where any prior use of escape medication/OL BI 655130 at D8/rescue medication with BI 655130 will be considered to represent a non-response) $>$ Placebo.

If the null hypothesis on GPPASI 75 at Week 4 has been previously rejected, then a test on the null hypothesis for the secondary endpoint, the pain VAS at Week 4, will be performed next in the testing hierarchy. The null hypothesis is:

H_{31} : Change from baseline in pain VAS at Week 4 for BI 655130 \geq Placebo (where negative change indicates an improvement from baseline);

versus the alternative hypothesis

H_{32} : Change from baseline in pain VAS at Week 4 for BI 655130 < Placebo (where negative change indicates an improvement from baseline).

If the null hypothesis on the pain VAS at Week 4 has been previously rejected, then a test on the null hypothesis for the secondary endpoint, the total score of PSS at Week 4, will be performed next in the testing hierarchy. The null hypothesis is:

H_{41} : Change from baseline in total score of the PSS at Week 4 for BI 655130 \geq Placebo (where negative change indicates an improvement from baseline);

versus the alternative hypothesis

H_{42} : Change from baseline in total score of the PSS at Week 4 for BI 655130 < Placebo (where negative change indicates an improvement from baseline).

If the null hypothesis on the PSS at Week 4 has been previously rejected, then a test on the null hypothesis for the secondary endpoint, the total score on the FACIT-Fatigue at Week 4, will be performed next in the testing hierarchy. The null hypothesis is:

H_{51} : Change from baseline in the total score on FACIT-Fatigue at Week 4 for BI 655130 \leq Placebo;

versus the alternative hypothesis

H_{52} : Change from baseline in the total score on FACIT-Fatigue at Week 4 for BI 655130 > Placebo.

Each of the above secondary endpoints will be tested in a hierarchical manner subsequent to rejection of the null hypothesis on the previous secondary endpoint hence no adjustment to the 1-sided alpha-level of 0.025 is necessary.

7.3 PLANNED ANALYSES

The primary analysis of this trial is planned to be performed once all randomized patients have completed the 12 week period or early discontinued from the trial; a database lock for the primary analysis will then be performed. Final analysis is planned to be performed at the end of the trial once all randomized patients have completed the trial (including any follow-up period) if applicable.

The primary analysis and final analysis may be performed as a single analysis (at the time of trial completion), if, prior to the time of the primary analysis, the trial team agrees that the expected time interval between the planned analyses is insufficient to justify the performance of separate analyses.

Details of treatment unblinding for the primary analysis and final analysis are described in [Section 4.1.5.1](#). Details of the analysis to be performed will be described in the TSAP.

There will be 3 main patient populations in this trial for analyses: the randomized set (RS), the safety set (SS), and the per-protocol set (PPS).

Randomized Set

This patient set includes all randomized patients. Treatment assignment will be as randomized. This is the main analysis set for presentation of efficacy.

Safety Set

This patient set includes all patients who were randomized and received at least one dose of study drug. It will be the main analysis set for presentation of safety. Patients will be analyzed according to the actual treatment.

Per-Protocol Set

This patient set includes all patients in the RS who adhered to the CTP without any Important Protocol Violations (IPVs) potentially affecting the study outcome which lead to exclusion from the PPS. This set will be used for sensitivity analysis on the primary, key secondary, and secondary efficacy endpoints which are included in the testing hierarchy.

Important violations of the protocol will include violations of the key inclusion and exclusion criteria, incorrect medications taken, concomitant use of restricted medications, escape medication given without evidence for disease worsening, and any other violations of the protocol deemed important by the study team. All decisions concerning important protocol violations will be made prior to un-blinding of the database for the final trial analysis.

Further analysis sets, e.g. for the BM assessments, will be defined in the Trial Statistical Analysis Plan (TSAP).

Standard statistical parameters (number of non-missing values, mean, standard deviation (SD), median, quartiles, minimum and maximum) or frequency tables (including patient frequencies and percentages) will be calculated where appropriate.

7.3.1 Primary endpoint analyses

The analysis for the primary endpoint includes the evaluation of patients achieving a GPPGA pustulation subscore of 0 at Week 1.

Any use of escape medication, e.g. use of restricted medication for disease worsening in [Table 4.2.2.1: 1](#), prior to observing the primary endpoint is considered to reflect a failure to achieve the endpoint outcome, i.e. non-response (see primary endpoint definition in [Section 2.1.2](#)).

Due to the small sample size of the trial, an exact statistical test will be used to assess the statistical significance of the treatment effect versus Placebo. Since the traditional Fisher's exact test may be unnecessarily conservative, an alternative test, the Suissa-Shuster Z-pooled test, will be implemented in this trial. The Suissa-Shuster Z-pooled test always preserves the type I error level and is usually more powerful than the Fisher's exact test.

The primary endpoint will be tested, for the RS, using the Suissa-Shuster Z-pooled test at a 1-sided, alpha level of 0.025.

Secondary analysis of the primary endpoint will include:

- A sensitivity analysis utilizing the PPS;
- Analysis of an additional estimand whereby any use of escape medication prior to week 1 will be considered to represent a non-response. For patients who use other restricted medication but not for disease worsening prior to Week 1, data will be censored for further analysis following the use and imputed using the methods described in [Section 7.5](#).
- Sensitivity analyses which utilize alternative methods for the handling of missing data as described in Section 7.5.
- A subgroup assessment according to the Japan vs. non-Japan strata will be assessed descriptively
- Sensitivity analyses to adjust for the covariates, IL36R mutation status (Yes vs. No) and baseline GPPGA total score (3 vs. 4) respectively using logistic regression.

Further analysis of the primary endpoint will include:

- Analysis of the time to first achievement of a response on the primary endpoint via Kaplan-Meier methods.

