[figure not shown]
[figure not shown]
[figure not shown]

Clinical Trial Protocol

Document Number:		c15875404-04
EudraCT No.: EU Trial No.:	2017-004231-37	
BI Trial No.:	1368-0013	
BI Investigational Product(s):	Spesolimab (BI 655130)	
Title:	Effisayil™ 1: Multi-center, double-blind, randomized, placebo-controlled, Phase II study to evaluate efficacy, safety and tolerability of a single intravenous dose of BI 655130 in patients with Generalized Pustular Psoriasis (GPP) presenting with an acute flare of moderate to severe intensity	
Lay Title:	A study to test BI 655130 in patients with a flare-up of a skin disease called Generalized Pustular Psoriasis	
Clinical Phase:	II	
Clinical Trial Leader:	

 Phone: [REDACTED]	
Coordinating Investigator:	

 Phone: [REDACTED] Fax: [REDACTED]	
Status:	Final Protocol (Revised Protocol (based on Global Amendment 2)	
Version and Date:	Version: 3.0	Date: 26 Jun 2020
Page 1 of 149		
Proprietary confidential information. © 2020 Boehringer Ingelheim International GmbH or one or more of its affiliated companies. All rights reserved. This document may not - in full or in part - be passed on, reproduced, published or otherwise used without prior written permission.		

CLINICAL TRIAL PROTOCOL SYNOPSIS

Company name	Boehringer Ingelheim
Finished product name	N/A
Active ingredient name:	Spesolimab (BI 655130)
Protocol date	27 June 2018
Revision date	26 Jun 2020
Trial number	1368-0013
Title of trial:	Effisayil™ 1: Multi-center, double-blind, randomized, placebo-controlled, Phase II study to evaluate efficacy, safety and tolerability of a single intravenous dose of BI 655130 in patients with Generalized Pustular Psoriasis (GPP) presenting with an acute flare of moderate to severe intensity
Coordinating Investigator:	 Phone:  ; FAX: 
Trial site(s):	Multi-center trial conducted in 11 to 20 countries.
Clinical phase:	II
Objective(s):	To evaluate efficacy, tolerability and safety of BI 655130 compared to placebo in patients with Generalized Pustular Psoriasis (GPP) presenting with an acute flare of moderate to severe intensity.
Methodology:	Multi-center, placebo-controlled, randomized, double blind
Number of patients entered:	51 patients
Number of patients on each treatment:	34 patients on BI 655130 and 17 patients on placebo

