The classic presentation of GPP flares as described by von Zumbusch is strongly correlated with polymorphisms in the IL36-R signaling pathway ([R15-1421](#), [R14-5158](#)). Individuals with loss-of-function mutations of the IL36RN gene which encodes an endogenous IL36R antagonist (IL-36RN) have dramatically higher incidence of GPP, indicating that uncontrolled upregulation of IL36 signaling due to defective IL36RN antagonism leads to the inflammatory episodes observed in GPP. Genetic human studies have demonstrated the occurrence of GPP clusters in families with a loss of function mutation in IL36RN, which results in uncontrolled IL36R signaling ([R14-5158](#)). Mutations in other genes linked to the IL36 pathway such as CARD14 ([R16-0929](#)) also lead to GPP. A recently published gene expression study indicates sustained activation of IL-1 and IL-36 in GPP, inducing neutrophil chemokine expression, infiltration, and pustule formation, suggesting that the IL-1/ IL-36 inflammatory axis is a potent driver of disease pathology in GPP ([R17-3602](#)). Moreover, a recent meta-analysis investigated 233 published GPP cases. They found that 49 (21.0%) of 233 cases carried recessive IL36RN alleles. Those 49 recessive IL36RN alleles defined a GPP phenotype characterized by early onset and high risk of systemic inflammation ([R16-0930](#)).

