7.7 DETERMINATION OF SAMPLE SIZE

Based on an application of the defined testing strategy (see [Section 7.2](#)), a simulation based power calculation has been performed for sample size assessment on both the primary and key secondary endpoints. For this purpose, the correlation of the two endpoints is set to be 0.65 which is derived from efficacy data of POC study 1368.11.

The effect of BI 655130 on the proportion of patients achieving a GPPGA pustulation subscore of 0 at Week 1 and separately on the proportion of patients achieving a GPPGA score of (0, 1) at Week 1 will be compared relative to placebo respectively. It is expected that, after one week of treatment with BI 655130, at least 60% of patients will have complete GPPGA pustulation subscore of 0 and at least 60% of patients will have a GPPGA score of 0 or 1. In comparison, only 10% of patients on placebo are expected to have response to each of the primary endpoint and key secondary endpoint at Week 1.

The power estimates below for detecting the clinically relevant differences, for the primary endpoint, the proportion of patients with a GPPGA pustulation subscore of 0 at Week 1 and the key secondary endpoint, a GPPGA score of 0 or 1 at Week 1, were derived using R version 3.3.2, for a sample size of 51 patients (2:1 ratio), and a 1-sided type I error of 0.025. The results are as given in [Table 7.7: 1](#).

Table 7.7: 1

Power to achieve statistical significance for the primary endpoint and key secondary endpoint on BI 655130 versus Placebo under various scenarios for N=51 (2:1)

Sample size: BI 655130 vs. placebo	Primary endpoint/Key secondary endpoint: Proportion of patients achieving GPPGA pustulation subscore of 0 at Week 1 [BI 655130 vs. placebo]/ Proportion of patients achieving GPPGA of (0 or 1) at Week 1 [BI 655130 vs. placebo]	Power (%) to achieve primary endpoint	Power (%) to achieve both primary endpoint and key secondary endpoint
34:17	0.5 vs 0.05/ 0.5 vs 0.05	95.7%	92.9%
34:17	0.55 vs 0.05/ 0.55 vs 0.05	98.1%	96.8%
34:17	0.6 vs 0.05/ 0.6 vs 0.05	99.4%	98.8%
34:17	0.65 vs 0.05/ 0.65 vs 0.05	99.9%	99.7%
34:17	0.5 vs 0.1/ 0.5 vs 0.1	85.3%	78.1%
34:17	0.55 vs 0.1/ 0.55 vs 0.1	92.0%	87.7%
34:17	0.6 vs 0.1/ 0.6 vs 0.1	96.3%	93.9%
34:17	0.65 vs 0.1/ 0.65 vs 0.1	98.5%	97.3%

Note: if the rates of response for both primary endpoint and key secondary endpoint were 0.55 on BI 655130 and 0.1 on placebo, separately, then the overall power to achieve both endpoints would be approx. 87.7%.

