- Sensitivity analyses on the RS to adjust for the potential covariates, IL36R mutation status (Yes vs No) and baseline GPPGA total score (3 vs 4) respectively.

The proportion of patients with a response between Spesolimab and placebo will be analysed by IL36R mutation status and baseline GPPGA total score (3 vs 4) respectively, using a logistic regression approach with a logit link via PROC LOGISTIC in SAS®. Fixed classification effects will include treatment, subgroup and treatment-by-subgroup interaction term.

The estimates from the logistic regression are on the logit scale, and the difference in proportions will be calculated as the difference between the predicted probabilities by subgroup level and treatment on the original scale.

Descriptive subgroup displays on the primary endpoint (via estimand EN) will be done for the applicable subgroups as defined in [Section 6.4](#) using the RS.

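### The SAP's interaction logistic models for the Week 1 sensitivity analyses have no finite maximum-likelihood estimate in about 67–94% of trials at the planned response rates, so their log-odds and Wald results are unusable

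*Protocol*

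**What the plan says.** Protocol 7.3.1 lists, among the secondary analyses of the primary endpoint, "Sensitivity analyses to adjust for the covariates, IL36R mutation status (Yes vs. No) and baseline GPPGA total score (3 vs. 4"), each handled separately by logistic regression. It mentions no interaction and no estimation method. Protocol 7.3.2 applies the same analyses to the key secondary endpoint.

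SAP 7.4 says the analysis is done "using a logistic regression approach with a logit link via PROC LOGISTIC in SAS" and that "Fixed classification effects will include treatment, subgroup and treatment-by-subgroup interaction term". It then converts the fit to differences in predicted probability between treatments within each covariate level. SAP 7.5.1 treats the key secondary endpoint in the same way. Neither section names a Firth, exact or other penalised fit, or a rule for separated data. The readable SAP refers to non-convergence methods (Section 9.2) only for the MMRM.

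The confirmatory analysis is separate: "The primary endpoint will be tested, for the RS, using the Suissa-Shuster Z-pooled test at a 1-sided, alpha level of 0.025".

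**The concern.** The interaction model for two treatments and a two-level covariate is saturated: it has four parameters for four cells. Its maximum-likelihood estimates are finite only if every cell contains at least one responder and one non-responder. Protocol 7.7 says "only 10% of patients on placebo are expected to have response to each of the primary endpoint and key secondary endpoint". With 17 placebo patients that is 17 × 0.10 = 1.7 expected responders, to be spread over two cells.

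When a cell has no responder, the coefficients run to infinity and the standard errors grow with each iteration. Whatever the software prints then depends on its stopping rule. If this is found only after unblinding, the remedy is chosen with the results in view. Protocol 1.3 says the trial will support first registration, so its sensitivity analyses will be read closely.

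**Working it through.** **Inputs**
- Arm sizes: "34 patients on BI 655130 and 17 patients on placebo" (Protocol synopsis).
- Response: 60% v 10% (Protocol 7.7). Table 7.7:1 also has a 5% placebo scenario.
- Test level: "for a sample size of 51 patients (2:1 ratio), and a 1-sided type I error of 0.025".
- Covariate share: not given for this trial. For mutation status, Protocol 1.1 reports of published cases: "They found that 49 (21.0%) of 233 cases carried recessive IL36RN alleles". I take 21% as an assumption and show 10% to 50% for either covariate. No split of baseline GPPGA 3 v 4 is given.
- Response is assumed independent of the covariate, with no missing covariate values.

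**Step 1: the plan's own figure.** Enumerating the Z-pooled test for 34:17 gives 96.3% power for the primary endpoint (stated: 96.3%). Simulation with correlation 0.65 gives 93.8% for both endpoints (stated: 93.9%). The inputs are therefore read correctly.

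**Step 2: placebo cells alone, fixed split.** With k and 17 − k placebo patients in the two covariate levels,

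P(at least one cell without a responder) = 1 − (1 − 0.9^k)(1 − 0.9^(17−k)).

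- k = 4 (about 21%): 1 − (1 − 0.656)(1 − 0.254) = 0.74.
- k = 8 (the most favourable split): 1 − (1 − 0.430)(1 − 0.387) = 0.65.
- At 5% placebo response and k = 8: 1 − (1 − 0.95^8)(1 − 0.95^9) = 0.88.

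With 0 or 1 placebo responders in total, one cell must be empty of responders. At 10% that probability is 0.9^17 + 17 × 0.1 × 0.9^16 = 0.167 + 0.315 = 0.48.

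**Step 3: all four cells, averaged over a binomial covariate split.** Percentage of trials without a finite estimate:

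| Model | Placebo rate | Share 10% | 21% | 30% | 50% |
|---|---|---|---|---|---|
| Interaction (SAP 7.4) | 10% | 94 | 80 | 73 | 67 |
| Main effects (Protocol 7.3.1) | 10% | 29 | 18 | 17 | 17 |

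At 5% placebo response the interaction model fails in 88–98% of trials (93% at a 21% share). The main-effects model fails whenever no placebo patient responds: 0.9^17 = 16.7%, or 0.95^17 = 41.8% at the 5% rate, so at least 42% there.

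**Step 4: what drives it.** At shares of 21% / 50% the interaction model fails in 100% / 100% of trials with 0 or 1 placebo responders, 70% / 50% with 2, and 55% / 25% with 3. By number of drug responders the rate is almost flat (79–81% / 67%).

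**Step 5: what breaks and what does not.**
- Interaction model, cells 16/27 and 4/7 on drug, 1/13 and 0/4 on placebo. The interaction coefficient has a standard error of about 14,600. The predicted risk differences are 0.516 and 0.571, equal to the observed 16/27 − 1/13 and 4/7 − 0/4.
- The interval around such a risk difference is still wrong. In a variant with placebo cells 0/4 and 2/13, the delta-method standard error for the 4/7 v 0/4 comparison is 0.187 = √[(4/7)(3/7)/7]. That is the drug cell's error alone, so the four placebo patients add no uncertainty.
- Main-effects model, 20/34 v 0/17 (cells 4/7, 16/27, 0/4, 0/13). The treatment Wald p-value is 0.40, 0.69, 0.86 and 0.94 at iterations 6, 8, 10 and 12. Firth's method gives a log odds ratio of 3.84 (profile interval 1.72 to 8.71), penalised likelihood-ratio p = 0.000015.

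**Step 6: Firth in the saturated model.** There it amounts to adding 0.5 to each outcome in each cell, so a cell proportion becomes (r + 0.5)/(n + 1). In the example 0/4 becomes 0.10 and 4/7 becomes 0.5625, and the risk difference falls from 0.571 to 0.463. In expectation at 60% v 10% with cells of 7 and 4: (4.2 + 0.5)/8 − (0.4 + 0.5)/5 = 0.5875 − 0.18 = 0.41, against a true 0.50.

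**The case against.** The only derived output SAP 7.4 names is the difference in predicted probabilities, and that converges to the raw subgroup difference even when coefficients diverge. The SAP names no Wald test or odds ratio for this model. In the 20/34 v 0/17 example an ordinary likelihood-ratio test gives p = 0.0000025, so the clash with the primary test comes only from using Wald results. SAP Section 9 is not in the readable text. These are sensitivity analyses outside the testing hierarchy. Firth applied to the interaction model would itself bias the reported risk differences.

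Much of this stands, and it rules out stronger readings that a reader might infer:
- That the robustness check fails outright. It does not: the point risk differences survive.
- That it fails exactly when the drug works best. At shares of 21% / 50% the failure rate does rise with the observed difference, from 57% / 33% below 0.4 to 96% / 93% at 0.6 or more. It barely moves with drug response, however. The driver is the placebo count.
- That most trials fail under the Protocol's wording. Most is true only of the SAP's interaction model.
- That the primary result is at risk. It rests on the unadjusted exact test.

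What the objection does not answer is that a point difference equal to the raw proportions adds nothing as an adjusted analysis. The plan gives no valid interval or test for it, and SAP 7.4 does not refer to Section 9.2.

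**Conclusion.** The concern holds for the log-odds estimates and any Wald standard error, interval or p-value from the SAP 7.4 models, for both Week 1 endpoints. At the planned 60% v 10% they are unusable in about 67–94% of trials for an assumed covariate share of 50% down to 10%. Whatever the split, the placebo cells alone put the figure at about 65% or more. With main effects only, the figure is about 17–18% for shares of 21–50%, about 29% at a 10% share, and at least 42% if the placebo rate is 5%.

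The figures rest on assumed covariate shares, on response being independent of the covariate, and on reading PROC LOGISTIC without options as ordinary maximum likelihood. The confirmatory test and the hierarchy are unaffected. This should be changed before unblinding, but it does not threaten the trial's main conclusion.

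**What to change.** In SAP 7.4, and through 7.5.1 for the key secondary endpoint:

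1. Estimate the covariate-adjusted treatment effect from a main-effects model (treatment plus one covariate) by Firth's penalised likelihood (the FIRTH option of PROC LOGISTIC). Report profile-penalised-likelihood confidence intervals and a penalised likelihood-ratio test in place of Wald results, for each of the two covariates. This also brings the SAP back to the adjustment worded in Protocol 7.3.1.
2. Report the by-subgroup risk differences from the observed proportions, with the Chan-Zhang exact intervals SAP 7.4 already uses for the primary endpoint. Do not take them from a Firth-fitted interaction model, which pulls small-cell proportions toward 50% (Step 6).

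The cost is one SAS option, removal of the interaction term and a few sentences of SAP text. The downside is slight shrinkage of the adjusted odds ratio. No new data are needed, and the sample size and the confirmatory analysis stay as they are.
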